
To begin to fill this research void, the aims of this pilot will be three-fold:

AIM 1: Determine the feasibility of making a lay patient navigator/care coordinator available to SLE inpatient admissions.

AIM 2: Determine the impact of making a lay patient navigator/care coordinator available to SLE inpatient admissions on disease self-management, disease activity, HRQOL, and readmissions as a marker of failed self-management.

AIM 3: Collect resource use and cost information to plan a well-designed economic study of the cost-effectiveness of the use of lay-navigators for SLE patients in the acute care setting.

This study will provide preliminary evidence on the cost-effectiveness of a lay patient navigator/care coordinator for patients with SLE. The immediate goal of proposed work is to provide pilot data on cost savings, cost effectiveness, and patient outcomes to refine approaches, service components, and measures, for future grants. Once effectiveness of the program is demonstrated, the long-term goal is to disseminate this potentially cost-effective approach in diverse clinical and community settings. The objectives of the proposed pilot project are directly responsive to high priority areas of national funding agencies. For example, the Patient-Centered Outcomes Research Institute (PCORI) is interested in funding projects that focus on improving patient-centered and clinical outcomes. National Institutes that traditionally fund lupus-related research such as NIDDK and NIAMS also have research objectives that include reducing the human and economic burden of diseases that disproportionately affect minorities. Proposed work also responds to initiatives that focus on self-management to reduce the burden of chronic illness. Thus, relevant future funding opportunities include R01-level calls such as PA-14-344 "Self-Management for Health in Chronic Conditions (R01)" and PA-16-007 "Personalized Strategies to Manage Symptoms of Chronic Illness (R01)"; PA-14-290 "ARHQ Health Services Research Demonstration and Dissemination Grants (R18)"; and PCORI Funding Announcement: Addressing Disparities.

B. BACKGROUND AND SIGNIFICANCE

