Treatment Fidelity. Drs. [name] and [name] will deliver training for the lay patient navigator/care coordinator at the onset of the study. They will be given parameters for their roles and instructed on how to handle potential issues that may arise. After the initial training, the lay patient navigator/care coordinator will continue to meet with the PI weekly to identify challenges and reinforce the guidelines for their role.[185] They will be required to submit logs of the number of calls made, number of hours spent with patients, and content covered during that week. Self-report assessments will be used to track the effectiveness of their services.

Data Collection Schedule. Study questionnaires were carefully chosen based on available evidence of previous validation and their ability to measure key elements of the study aims. The primary method of data collection will be face-to-face interview. All study visits will take place in an MUSC affiliated hospital, the Research Nexus or comparable private location on the campus of MUSC. Indicators of medication adherence will be extracted from the electronic medical records. Financial data will be extracted from the research data warehouse for historical and patient-specific data for cost effectiveness. The MUSC REDCap system will be used for data management.

Primary Outcomes. Primary outcomes of quality of life, self-management, and disease activity (including medication adherence) will be measured using the Lupus Quality of Life Questionnaire (LUP-QOL), which incorporates the Medical Outcomes Study (MOS) Short Form 36 Health Survey (SF-36) and the Functional Assessment of Chronic Illness Therapy-Fatigue (FACIT-F);[187-189] the Patient Activation Measure (PAM), [190,191] which assesses an individual's knowledge, skill, and confidence for managing their health and healthcare; medication refill data in electronic medical records to further validate treatment engagement/adherence; 30-day readmission data to assess cost savings or deficit (compared to historical data from the prior year); and the Systemic Lupus Activity Questionnaire (SLAQ),[192] which is based on items from the physician-rated Systemic Lupus Activity Measure (SLAM) that could be self-reported.[193,194]

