Aim 3 – Collection of resource use and cost information: With a total of 40 patients, and 20 patients in the intervention group, we expect a maximum of 6-8 readmissions over 30 days. If the readmission rate was reduced from 20% to 15%, there would only be about 7% power to detect a difference. Further, the mean cost of lupus admissions is about \$17,000, but the SD of these costs is around \$30,000, which indicates that it is not feasible to expect to detect a difference in cost between the groups. However, there is a large amount of resource use and cost information that will be collected to inform a well-designed economic study of the cost-effectiveness of the use of lay-navigators for SLE patients in the acute care setting. To plan a larger trial with an economic component, the following pilot data will be collected: 1) resource use and cost of training the navigator; 2) cost of use of the navigator for 12 weeks; 3) any issues related to recidivism of patients once they no longer have the navigator support; 4) association between length of stay (LOS) of the initial admission and subsequent readmissions; 5) total number of admissions and days in the hospital for the 12 week intervention period (some patients have more than one readmission within 30 days of discharge and at least 50% of readmissions over 90 days happen after the 30-days benchmark); 6) use of other services, such as ER visits; 6) distributions of cost for the medical care resources used; 7) other medical care resources of importance to patients; 8) economic and financial barriers to use of care outside the hospital setting; and 9) how much of the care resources that patients use during the study period is missed because patients get care from other hospitals or entities who are not part of the MUSC record system. For collection and analysis of pilot data, resource use and cost data will be accessed through the Services, Pricing, and Application for Research System (SPARC Requests), which is available to MUSC-based investigators under MUSC's Clinical and Translational Science Award (CTSA). The system allows for easy access to pricing for services across the MUSC campus and its providers and focuses on billing compliance and budgetary analysis. In order to extract data from the MUSC record systems, services are requested through an online portal and data is then provided through direct consultation. Within the SPARC system, members of the study team will also be able to track service utilization and pricing throughout the duration of the study.

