3. POTENTIAL BENEFITS OF THE PROPOSED RESEARCH TO THE SUBJECTS AND OTHERS

- *Discuss the potential benefits of the research to the subjects and others.*

- *Discuss why the risks to subjects are reasonable in relation to the anticipated benefits to subjects and others.*

The overarching aims of this pilot project is to provide preliminary evidence on the cost-effectiveness of a lay patient navigator/care coordinator in forty (40) systemic lupus erythematosus (SLE) patients, targeting inpatient admissions to prevent readmissions as a marker of failed self-management. Our rationale is that a lay patient navigator/care coordinator integrated into the health care team to provide modeling and reinforcement to SLE patients will encourage patients to engage in activities that promote the learning of disease self-management skills and support their practice of these learned skills.

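### The primary-outcome text uses 30-day readmission to assess a cost saving or deficit, which the Aim 3 figures cannot support

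*Protocol*

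**What the plan says.** Protocol section D, Primary Outcomes, lists the quality-of-life, activation, refill and disease-activity measures together with "30-day readmission data to assess cost savings or deficit (compared to historical data from the prior year"). Readmission is thus a primary outcome, its stated use is a cost assessment, and its comparator is the previous year's records.

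The Analysis Plan for Aim 3 says what the trial can deliver on the same data. It begins "With a total of 40 patients, and 20 patients in the intervention group, we expect a maximum of 6-8 readmissions over 30 days", then states "If the readmission rate was reduced from 20% to 15%, there would only be about 7% power to detect a difference". It gives an admission cost of about USD 17,000 on average with an SD of around USD 30,000, and concludes that "it is not feasible to expect to detect a difference in cost between the groups". It then lists resource-use and cost items to be gathered for designing a larger trial. That list contains no savings assessment and no comparison with prior-year data.

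Elsewhere the protocol speaks of preliminary evidence. The aims section says "This study will provide preliminary evidence on the cost-effectiveness of a lay patient navigator/care coordinator for patients with SLE", and section E.3 repeats the idea as an overarching aim.

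**The concern.** The Primary Outcomes paragraph assigns readmission data a use that the Aim 3 paragraph says the trial is too small to serve. A reader cannot tell whether a statement of savings or deficit is a primary result of this pilot or has been ruled out in advance.

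The protocol means to use its cost and outcome data to refine the programme for future grants, and its opening summary links assessment of cost effectiveness to the case for sustaining the service. If the observed difference were reported as a saving or a deficit, its direction would be mostly noise. The historical comparison has a further weakness. Hospital costs are usually right-skewed, so the mean of a small sample falls below the true mean more often than above it. A stable historical average would then tend to make the pilot look cheaper even if the navigator did nothing.

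**Working it through.** **Inputs from the protocol (section D, Aim 3):** 20 patients per arm; readmission 20% against 15%; admission cost mean USD 17,000, SD USD 30,000; stated power about 7%.

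**Assumptions, not in the protocol:** two-sided alpha 0.05 for the power figure; at most one readmission per patient; gross readmission cost only, without the navigator's cost; historical mean known without error; lognormal costs where stated.

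**1. The stated power.** Two-proportion z-test, pooled rate 0.175:
- SE under the null = sqrt(0.175 × 0.825 × 2/20) = 0.1202
- SE under the alternative = sqrt(0.20 × 0.80/20 + 0.15 × 0.85/20) = 0.1199
- Upper tail: Φ((0.05 − 1.96 × 0.1202)/0.1199) = 0.061
- Lower tail: Φ((−0.05 − 1.96 × 0.1202)/0.1199) = 0.009
- Total 0.070

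Exact power of the uncorrected chi-square test is 6.9%. The protocol's 7% is correct. The expected count also fits: 15% to 20% of 40 patients is 6 to 8.

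**2. Readmission cost per patient.** Mean = p × 17,000; variance = p × (30,000² + 17,000²) − (p × 17,000)².
- p = 0.20: mean 3,400, SD 15,041
- p = 0.15: mean 2,550, SD 13,109
- Expected saving = 3,400 − 2,550 = USD 850 per patient

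**3. The 95% margin around that saving.**
- Between arms: SE = sqrt((15,041² + 13,109²)/20) = 4,461; 1.96 × 4,461 = USD 8,744, about 10 times the saving.
- Intervention arm against a fixed historical mean: SE = 13,109/sqrt(20) = 2,931; 1.96 × 2,931 = USD 5,745, about 7 times the saving.
- With 20% readmission in both arms and a t multiplier, the between-arm margin is 2.024 × 15,041 × sqrt(2/20) = USD 9,627, about 11 times the saving.

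**4. How often the result points to a saving.** The normal columns are Φ(saving/SE). The lognormal columns come from 200,000 simulated trials with cost = Bernoulli(p) × lognormal(mean 17,000, SD 30,000).

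| Comparison | No effect, normal | No effect, lognormal | 20% to 15%, normal | 20% to 15%, lognormal |
|---|---|---|---|---|
| Against fixed historical mean | 50% | 64% | 61% | 76% |
| Between arms | 50% | 50% | 58% | 61% |

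**5. Sensitivity to navigator cost.** The protocol collects this cost but gives no figure. In the lognormal model with no effect, the chance of an apparent net saving is:

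| Assumed navigator cost per patient | Against historical mean | Between arms |
|---|---|---|
| USD 0 | 64% | 50% |
| USD 500 | 56% | 43% |
| USD 1,000 | 48% | 36% |
| USD 2,000 | 27% | 26% |

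**6. Readmission counts alone.** For 20 patients against a fixed 20%, a true rate of 20% gives fewer than expected in 41% of trials, a tie in 22% and more in 37%. A true rate of 15% gives 65%, 18% and 17%. An observed 3/20 has an exact 95% interval of 3% to 38%.

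**The case against.** The strongest reply is that the limitation is already disclosed. Aim 3 states the low power, says a cost difference is out of reach and turns the economic work into planning. To assess a saving or deficit is compatible with an estimate and an interval. Much of this stands, and it rules out several stronger readings:

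- **That the protocol will declare a saving or a deficit by the sign of the difference.** No decision rule appears anywhere. The percentages above describe how little the direction tells, not how often the trial would announce a saving.
- **That no error margin is planned.** The Aim 2 plan promises 95% confidence intervals for outcome variables. Its explicit list omits readmission, and its change-from-baseline mixed model does not fit a 30-day event. But this is silence that a statistical analysis plan could fill.
- **That the result is a coin toss.** That roughly fits the between-arm comparison, but the Primary Outcomes paragraph names the historical one. There the figure with no effect is 50% or 64% depending on skewness, and lower once navigator cost is included.
- **That Aim 3 rules out the historical comparison in terms.** Its statement concerns the two groups only. The historical margin in step 3 has to carry that part of the argument.
- **That every mention of preliminary cost-effectiveness evidence contradicts Aim 3.** This is ordinary pilot language and promises no conclusion.

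The calculations are also simplified. The protocol notes that some patients are readmitted more than once within 30 days, which would change the spread, and uncertainty in the historical mean would widen the margin.

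The reply does not remove the mismatch itself. A primary outcome is given a cost-assessment use, while the analysis text for the same data limits it to planning. An interval in a separate plan would not settle which of the two governs.

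**Conclusion.** The point holds as an inconsistency about what the pilot may conclude. The savings-or-deficit use in Primary Outcomes is not supported by the protocol's own figures: an expected saving of about USD 850 per patient sits inside a 95% margin of about USD 8,700 between arms, or about USD 5,700 against an error-free historical mean. Under lognormal costs the historical comparison also leans towards an apparent saving when there is none. That lean depends on the skewness assumption and on leaving out navigator cost, and at an assumed USD 1,000 per patient it is gone (48%). The margins do not depend on the lognormal assumption, but they do rest on 20 per arm and at most one readmission per patient.

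The protocol's 7% power figure is right. The finding does not show that the trial would report a false saving, and the preliminary-evidence wording in the aims, Innovation, E.1 and E.3 can stay as it is.

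**What to change.** In section D, Primary Outcomes, replace the clause on assessing cost savings or deficit against the prior year. The new text should say that:

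- 30-day readmission and its cost are reported by randomised arm with 95% confidence intervals (bootstrap for cost), as planning inputs under Aim 3;
- any comparison with historical data is descriptive only;
- no conclusion of savings or deficit will be drawn from this pilot.

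This is a wording change in one paragraph. Data collection, sample size and the other outcomes are unaffected. The cost is that the pilot gives up a cost-savings statement, which the Aim 3 text already concedes it cannot support.

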Overview of Study Design. The Care-coordination Approach to Learning Lupus Self-Management (CALLS) study is a double arm, pre-post pilot designed to examine whether modeling and reinforcement from a lay patient navigator/care coordinator improves disease self-management, indicators of disease activity, health related quality of life (HRQOL), and 30-day readmission in SLE inpatient admissions. We will recruit 40 patients (20 questionnaires and phone sessions and 20 questionnaires only) with active SLE upon hospital admittance at the Medical University of South Carolina (MUSC). The lay patient navigator/care coordinator will be trained to deliver intervention content by twelve weekly telephone sessions carried out across the course of the study. All participants will be assessed using validated measures of patient reported outcomes at baseline, mid-intervention (6 weeks post-enrollment), and immediately following the intervention (12 weeks post-enrollment). Outcomes for patients who agree to phone sessions will be compared with the outcomes of patients who opt to participate in questionnaires only. The study will last 12 months with recruitment and enrollment over 6 months, 3 months for intervention delivery and 3 months for data analysis.

Study Population. The total number of individual patients with systemic lupus erythematosus (SLE) currently being followed by clinicians at MUSC is 1,159 in the past six months that had this encounter diagnosis and 1,526 with this diagnosis in the chart history or problem list or encounter diagnosis, of which approximately 60% are African American and 90% are female. This will allow for the assessment of impact and cost savings/effectiveness according to underrepresented racial and gender categories. The target population for this study will be SLE inpatient admissions. There are approximately 35 SLE and Scleroderma hospital admissions each month, so it is expected that over a 3-month recruitment period, we will be able to recruit 40 participants (20 questionnaires and phone sessions and 20 questionnaires only).

Recruitment of Lay Patient Navigator/Care Coordinator

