Admitted SLE patients will be referred by their physician for participation in the study, who will provide a letter that will explain the study and provide participants a number to call if they have questions or concerns prior to agreeing to participate. Participants who indicate interest in the study will be immediately screened for eligibility, and if eligibility criteria are met, informed consent will be obtained. Once a patient has been consented, they will be randomized to membership in one of the two study arms. assigned to the intervention (complete questionnaires and phone sessions) or control (complete questionnaires only) arm, and the rest of the recruitment visit will include baseline self-report assessments and scheduling of phone sessions (if applicable). Preliminary data from our group suggests that those participants with the worse outcomes at baseline experienced the largest gains post-intervention, so the proposed intervention focuses on patients with high needs (as indicated by hospital admission) to reach those with the greatest potential for benefit from supportive services. This approach could ultimately incorporate the lupus nephritis risk prediction model/tool being developed by [name] to prevent renal failure and admissions due to renal flares.

Inclusion criteria for SLE patients include: 1) Hospital admission for SLE-related issue; 2) clinical diagnosis of systemic lupus erythematosus (SLE) from a physician; 3) 18 years of age or older; 4) able to provide informed consent and take part in ongoing assessment/evaluation activities (self-reported questionnaires); 5) able to commit to duration of study (3 months); 6) able to communicate in English; and 7) have an active phone line (landline or cell phone) for the duration of the study, if agreeing to phone sessions with the lay patient navigator/care coordinator. Exclusion criteria include: 1) cognitive impairment; 2) acute decompensation of chronic conditions precluding participation; 3) conditions that preclude participation in assessments (e.g. blindness or deafness); and 4) terminal illness or life expectancy less than 6 months as evaluated by physician.

Lay Patient Navigator/Care Coordinator Service Elements.

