Aim 2 - Estimation of effect sizes for calculating sample size for future R01: Analyses for Aim 2 of the pilot/feasibility study will focus on estimation of preliminary effectiveness as determined by: (a) change in quality of life; (b) change in self-management; and (c) change in disease activity (self-reported). Estimates of effect sizes for outcome variables will be reported as point estimates (mean differences between pre-post measures, as appropriate) and interval estimates (95% CI) to provide a preliminary indication of the presence of a clinically important treatment effect.[201-203] After studying the distributions of baseline characteristics, we will use a linear mixed-effects regression model to estimate the difference in the change from baseline between the two groups. Least squares means for each outcome variable will be compared at the primary time point (week 12) and at intermediate time points (week 6 or 12) using model contrasts to estimate the corresponding 95% CI for the estimates of the difference in outcome means (effect sizes) between and within treatment group.

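### Aim 2 gives within-arm pre-post changes the same label and purpose as the randomised between-arm contrast, although patients enrolled with active lupus during an admission may improve without the navigator

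*Protocol*

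**What the plan says.** The Aim 2 paragraph of the Analysis Plan (Protocol, section D) is titled "Estimation of effect sizes for calculating sample size for future R01". It reports point estimates as "mean differences between pre-post measures, as appropriate", with 95% intervals, and gives their purpose as "to provide a preliminary indication of the presence of a clinically important treatment effect". It then plans a linear mixed model to "estimate the difference in the change from baseline between the two groups", with week 12 as the primary time point, and obtains 95% intervals "for the estimates of the difference in outcome means (effect sizes) between and within treatment group".

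The Sample Size Justification keeps both roles. It states the Aim 2 goal as the change in LUP-QOL within and between arms, and gives a precision for each: 0.57 SD within an arm and 0.64 SD between arms.

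On enrolment, the inclusion criteria require "Hospital admission for SLE-related issue", and the Overview of Study Design describes patients "with active SLE upon hospital admittance". The baseline questionnaires are completed at the recruitment visit, and follow-up is at 6 and 12 weeks. Nowhere does the protocol say that a within-arm change is descriptive or cannot be attributed to the navigator.

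**The concern.** Patients selected because they are ill enough to be in hospital, and measured again 6 and 12 weeks later, may well look better whatever is done for them. Part of that is recovery from the episode; part is regression to the mean. A pre-post change in one arm cannot separate either from the effect of the phone sessions. Here the plan does more than report such changes: it calls them effect sizes and ties them to the presence of a treatment effect.

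Two things are at stake. The pilot could report an encouraging effect for an intervention that does nothing. And because the paragraph does not say which effect size goes forward, an analyst following it to the letter could size the next trial on a pre-post difference.

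The recruitment section adds to the worry. It justifies enrolling inpatients by noting that "those participants with the worse outcomes at baseline experienced the largest gains post-intervention", a pattern that regression to the mean also produces.

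**Working it through.** **What each estimate measures.** Let R be the mean change from baseline to week 12 that would occur without the navigator, and D the navigator effect.

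- Navigator arm, pre-post change: R + D
- Control arm, pre-post change: R
- Between-arm difference in change: (R + D) − R = D

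Only the last isolates D, provided the arms are randomised. A within-arm change equals D only if R = 0, which the protocol neither states nor makes likely for patients admitted with active disease.

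**The plan's own precision.** Inputs from the Sample Size Justification: 20 per arm, three time points, AR(1) correlation with ρ = 0.5, two-sided 95% interval.

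- Correlation from baseline to the third time point: r = 0.5² = 0.25
- SD of change: √(2(1 − r)) = √1.5 = 1.225 SD
- Standard error within an arm: 1.225/√20 = 0.274 SD
- Half-width: t(0.975, 19 df) × 0.274 = 2.093 × 0.274 = 0.573 SD

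This reproduces the stated 0.57. So if an arm improved by about 0.57 SD for reasons unrelated to the navigator, its interval would on average just reach zero.

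**Illustration with D = 0.** The documents give no figure for R, so everything here rests on an assumed shift s, the amount by which admission scores are worse. The chance that the within-arm interval excludes zero comes from the noncentral t distribution with 19 df and noncentrality (mean change)/0.274. Two mechanisms are possible, and they give different answers.

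1. *Return to the usual level.* Scores at admission are s worse than usual and recover fully, so the mean change is s.
   - s = 0.5: noncentrality 0.5/0.274 = 1.83; the interval excludes zero in about 41% of trials.
   - s = 1.0: noncentrality 1.0/0.274 = 3.65; about 93%.
2. *Selection on an extreme observed score.* The mean change is s(1 − r).
   - r = 0.25: s = 0.5 gives 0.375 SD and about 26%; s = 1.0 gives 0.75 SD and about 74%.
   - r = 0.5: s = 0.5 gives 0.25 SD and about 19%; s = 1.0 gives 0.50 SD and about 56%.

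In every case the randomised between-arm difference has expectation zero, and its 95% interval excludes zero in 5% of trials.

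**Precision of the between-arm estimate.** Half-width = t(0.975, 38 df) × SD of change × √(2/20).

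- r = 0.25: 2.024 × 1.225 × 0.316 = 0.78 SD
- r = 0.5: 2.024 × 1.000 × 0.316 = 0.64 SD

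The plan's 0.64 therefore needs r = 0.5, while its 0.57 needs r = 0.25. On the r = 0.25 basis the comparison is 0.78 between arms against 0.57 within.

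**The case against.** The best defence is that the valid analysis is already there. The mixed model targets the between-arm difference in change, week 12 is named as the primary time point, the Sample Size Justification includes the treatment-by-time interaction, and a between-arm precision is given. The pre-post phrase is a parenthesis qualified by an as-appropriate clause. Showing the change in both arms side by side would also expose natural recovery. All of this stands, and it limits the point to labelling and use.

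A reader might infer more than the text supports:

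- *That the study lacks a controlled comparison, or that the pre-post figure is its headline.* Neither is so; within-arm and between-arm estimates are named together.
- *That the R01 will be sized on natural recovery.* The heading says effect sizes will inform it, not that within-arm ones alone will.
- *That the group's earlier data show untreated improvement.* The sentence about patients worst at baseline concerns gains after an intervention. It fits regression to the mean, but also a larger true benefit in high-need patients, which is how the protocol reads it.
- *That every outcome would improve unaided.* This is plausible for disease activity and quality of life, less so for patient activation, which measures knowledge, skill and confidence.

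What the defence does not answer is that the protocol fixes an interpretation. Calling within-arm contrasts effect sizes that point to a treatment effect is a statement made in the text, not a detail left open for an analysis plan.

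**Conclusion.** The point holds as one of role and wording. Within-arm pre-post changes should not carry the label or purpose of a treatment effect in a study that enrols patients with active disease during an admission. A controlled comparison is not missing.

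The size cannot be derived from the documents, because they give no expected untreated change. The 19% to 93% span above illustrates assumed shifts of 0.5 to 1.0 SD under two mechanisms and should not be quoted as an estimate for this trial. What does not depend on those assumptions is the algebra: a within-arm change includes any untreated change, and the randomised contrast removes it.

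The conclusion assumes that assignment is random, as the recruitment section says. The Overview of Study Design instead describes patients who agree to phone sessions or opt for questionnaires only. If the arms were self-selected, the between-arm contrast would not be clean either, so that wording needs to be reconciled.

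**What to change.** In the Aim 2 paragraph, define the treatment-effect estimate as the between-arm difference in change from baseline at week 12 (the treatment-by-time contrast) with its 95% interval, and state that this is the only effect-size input to the R01 sample size. Report within-arm pre-post changes for both arms as description, and remove the effect-size label and the treatment-effect purpose from them.

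Make the same change in the Sample Size Justification, where the Aim 2 goal names within-arm and between-arm change together. That sentence also sets the time point at 12 months after the intervention, while the rest of the protocol ends at week 12; align it in the same edit.

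The cost is wording only: no new data, visits or model. The downside is precision. The between-arm interval is wider than the within-arm one (0.78 against 0.57 SD at r = 0.25, or 0.64 between arms as the plan states it), so the pilot will give the R01 a less certain figure.
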